- SCORAD Total Score = [Overall BSA affected by AD / 5] + [Intensity score * 7/ 2] + Subjective symptoms score (i.e., pruritus + sleep loss), ranging from 0 to 103. SCORAD total score will be set to missing if information for any of the three measures is missing.
- Change from baseline = Assessment value at post-baseline visit X – baseline value.
- Percent change from baseline = (Assessment value at post-baseline visit X – baseline value) × 100% / (baseline value)

Percent change from baseline will be missing in situation where baseline value equals to 0.

- Exposure-adjusted incidence rate (EAIR) = (number of subjects with an event / total within-arm exposure [days]) * 365.25 days/year * 100.
- BMI (kg/m²) = (weight in kg)/ [(height in cm/100)²]. For child and adolescent (2 to 17 years), after BMI is calculated, it is expressed as a percentile using data files and instructions provided by the CDC (https://www.cdc.gov/growthcharts/percentile_data_files.htm).

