5.6 Descriptive Statistics

All continuous variables will be summarized by presenting the number of subjects ('n'), mean, standard deviation (SD), median, Q1, Q3, minimum, and maximum. For PK endpoints, the coefficient of variation (CV), geometric mean, and geometric CV will also be provided.

Categorical variables will be presented as frequencies and percentages. The AE tables will also present the within-arm summary measure of EAIR; expressed as number of subjects with events per 100 subject exposure years.

 Innovaderm Research 	STATISTICAL ANALYSIS PLAN, Final Version 1.0
Protocol Number: ARQ-151-313	Sponsor: Arcutis Biotherapeutics, Inc.

Summary tables will be presented by visit, when applicable, and treatment group (refer to Section 5).

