13.1 Adverse Events

AEs will be coded according to the latest available version of MedDRA (Version 25.0 or higher).

A treatment emergent adverse event (TEAE) is defined as an AE that started post application of study medication at the Day 1 visit of study ARQ-151-313 or was present at treatment initiation but worsened during treatment, through study completion. See [Appendix 2](#) for handling of completely or partially missing dates for AEs. In the case where it is not possible to define an AE as treatment emergent or not, the AE will be classified as treatment emergent.

An overall summary of TEAEs will be presented by treatment group as defined in Section 5, which will include the total number of events, and the number and percentage of subjects who experienced at least one TEAE, TEAE by the maximum severity, TEAE by relationship and TEAE by the strongest relationship, treatment-emergent SAE, treatment-emergent Non-SAE, TEAE leading to study treatment discontinuation, TEAE leading to study discontinuation, TEAE on an application site, and TEAE leading to death. In addition, similar summary as described above will be presented by age group (refer to Section 6.6) for rollovers from study ARQ-151-311/312.

The number and percentage of subjects who experience at least one TEAE will be summarized by SOC, PT, and treatment group as defined in Section 5. A subject experiencing the same TEAE multiple times within the same PT will be counted only once for that PT. Similarly, a subject experiencing the same TEAE multiple time within the same SOC will be counted only once for

 Innovaderm Research	STATISTICAL ANALYSIS PLAN, Final Version 1.0
Protocol Number: ARQ-151-313	Sponsor: Arcutis Biotherapeutics, Inc.

that SOC. TEAEs will be sorted alphabetically by SOC and within each SOC, the PT will be presented by descending frequency. In addition, similar summary as described above will be presented by age group (refer to Section 6.6) for rollovers from study ARQ-151-311/312.

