The number and percentage of subjects who experience at least one TEAE will also be summarized by SOC, PT, strongest relationship with study treatment (related or not related) and treatment group. A treatment-related TEAE is defined as any TEAE that is assessed by the Investigator as likely, probably, or possibly related to study treatment. TEAE that is assessed as unrelated or unlikely will be defined as not treatment-related. If a subject experiences more than one TEAE within different relationship categories within the same SOC/PT, only the worst case (the strongest relationship) will be reported. TEAE with an unknown relationship will be considered as treatment-related.

The number and percentage of subjects who experience TEAE will also be summarized by SOC, PT, maximum severity (mild/moderate/severe/life threatening/death related to AE), and treatment group as defined in Section 5. If a subject experiences more than one TEAE within different severity categories within the same SOC/PT, only the worst case (the maximum severity) will be reported. TEAE with an unknown severity will be considered as severe.

The number and percentage of subjects who had treatment-emergent SAE will be summarized by SOC, PT, and treatment group as defined in Section 5. TEAEs leading to study drug discontinuation and TEAEs leading to study discontinuation will be summarized similarly.

Frequency and percentage of subjects who experience TEAE on an application site will be summarized by SOC, PT, and treatment group as defined in Section 5.

A plot of most frequent TEAE ($\geq 1\%$) will be provided by PT and treatment group as defined in Section 5 (overall TEAE and overall treatment-emergent SAE will be included in the same plot).

The EAIR and the corresponding 95% CI will be reported for all tables of TEAEs by SOC and PT described earlier in this section. The EAIR per 100-pt year, defined in Section 5.5, will be calculated in each arm and the 95% CI will be calculated by using a Poisson regression model with number of TEAEs as dependent variable and log of exposure time as offset. Additionally, the difference in EAIR between the 'Roflumilast cream 0.15%' and 'Vehicle / Roflumilast cream 0.15%' treatment groups (refer to Section 5) will be provided along with the associated two-sided 95% CI.

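### SAP 13.1 takes the 95% CI for the EAIR from a model of TEAE counts, although the EAIR counts subjects with an event

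*SAP*

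**What the plan says.** SAP 5.5 gives the EAIR as ("number of subjects with an event / total within-arm exposure [days]) * 365.25 days/year * 100". SAP 5.6 repeats the unit for the AE tables: "expressed as number of subjects with events per 100 subject exposure years". Both put subjects, not events, in the numerator.

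SAP 13.1 then commits to the interval: "The EAIR and the corresponding 95% CI will be reported for all tables of TEAEs by SOC and PT described earlier in this section". It refers back to Section 5.5 for the rate, but obtains the interval from a "Poisson regression model with number of TEAEs as dependent variable and log of exposure time as offset".

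Three other statements in SAP 13.1 bear on how to read this:

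- In the main SOC/PT table, a subject with repeated occurrences of a preferred term "will be counted only once for that PT", with a similar rule for each SOC.
- In the relationship table "only the worst case (the strongest relationship) will be reported", and in the severity table "only the worst case (the maximum severity) will be reported".
- The overall TEAE summary lists "the total number of events, and the number and percentage of subjects who experienced at least one TEAE", so it reports events and affected subjects as separate counts.

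SAP 13.1 also promises a two-sided 95% CI for the difference in EAIR between the two previous-treatment groups from ARQ-151-311/312. It names no method for it.

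**The concern.** A Poisson model with a log-exposure offset estimates the total of its outcome variable divided by total exposure. If the outcome is the number of TEAEs, the model estimates events per patient-year. The EAIR is affected subjects per patient-year. The two coincide only in rows where nobody has more than one TEAE. Elsewhere, the table would print a point estimate of one quantity beside an interval for another.

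TEAEs and SAEs are the primary endpoints, and under SAP 13 the EAIRs are the only safety results that receive confidence intervals. The exposure is most visible in the all-TEAE SOC/PT table, its age-group version and the application-site table, in SOC rows and frequent preferred terms. In those rows the interval is shifted upwards and can exclude the rate it accompanies.

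**Working it through.** The plan states no EAIR, event count or exposure total, so there is no figure of its own to reproduce. The check compares the two definitions.

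**Notation.** s is the number of affected subjects in a row, m is the mean number of TEAEs per affected subject, and T is total exposure in years.

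**Rates (per 100 patient-years).**
- EAIR (SAP 5.5): 100 × s/T.
- Rate estimated by the model in SAP 13.1, read literally: 100 × s·m/T = m × EAIR.

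**Wald limits on the log scale, as multiples of the EAIR.**
- Matching interval (outcome is affected subjects): exp(∓1.96/√s).
- Literal interval (outcome is TEAEs): m × exp(∓1.96/√(s·m)).

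T cancels, so no assumption about enrolment or follow-up is needed. The limits assume an unscaled Poisson variance.

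| s | Matching (m = 1) | Literal, m = 1.2 | Literal, larger m |
|---|---|---|---|
| 100 | 0.82 to 1.22 | 1.003 to 1.44 | 1.09 to 1.54 (m = 1.3) |
| 20 | 0.65 to 1.55 | 0.80 to 1.79 | 1.05 to 2.15 (m = 1.5) |
| 10 | 0.54 to 1.86 | 0.68 to 2.11 | 1.29 to 3.10 (m = 2) |

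Worked entry, s = 100 and m = 1.2: √120 = 10.954 and 1.96/10.954 = 0.1789, so the limits are 1.2 × exp(−0.1789) = 1.003 and 1.2 × exp(0.1789) = 1.44.

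**When the EAIR falls below its own lower limit.** Solve m × exp(−1.96/√(s·m)) = 1:

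| s | 200 | 100 | 50 | 20 | 10 |
|---|---|---|---|---|---|
| m | 1.14 | 1.20 | 1.28 | 1.44 | 1.63 |

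**Example on assumed data:** 300 patient-years, 200 affected subjects, 300 events (m = 1.5).
- EAIR = 200/(300 × 365.25) × 365.25 × 100 = 66.7.
- Poisson regression on a 0/1 outcome: 66.7 (58.0 to 76.6).
- Poisson regression on event counts: 100.0 (89.3 to 112.0), which excludes 66.7.

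**Check of the offset**, on a synthetic arm of 950 subjects with unequal exposure, 100 affected subjects and 130 events (m = 1.3):
- 0/1 outcome, each subject's own exposure as offset: 17.49 (14.37 to 21.27).
- A single count of 100, arm-total exposure as offset: 17.49 (14.37 to 21.27), the same.
- 0/1 outcome with the arm total placed on every record: 0.0184, which is 17.49/950 and therefore wrong.
- Event counts, own exposure as offset: 22.73 (19.14 to 27.00), which excludes 17.49.

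**The case against.** The strongest reply is that the context shows what was meant. The sentence that names the model also names the Section 5.5 rate as its target, SAP 5.6 repeats the subject-based unit, and the tables concerned count a subject once per SOC and once per preferred term. On that view, the model's TEAE count is loose wording for affected subjects, since nobody would plan an interval that can exclude its own estimate. The separate event total appears in the overall summary, which is not one of the SOC/PT tables.

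This may well be the authors' intention. But the count-once rules govern what is tabulated, and nothing carries them into the regression. Two programmers could follow SAP 13.1 faithfully and produce different intervals.

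Other points stand as limits on size:

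- m is not given, and Protocol 5.7.1 keeps ordinary progression of atopic dermatitis out of AE reporting, which removes one source of repeat events.
- The effect is small or nil for rare preferred terms and for most SAE and discontinuation rows. The same holds for the relationship and severity tables if the model uses the worst case per subject that they report.
- The SAP does not say whether dispersion is scaled. If it were, and affected subjects had one or two events each, the thresholds would rise to about 1.88 (10 affected), 1.58 (20), 1.34 (50), 1.23 (100) and 1.16 (200). That matters for small rows and little for the frequent rows where the problem lies.
- Poisson variance on a 0/1 outcome is somewhat conservative in common rows, so the matching interval is itself approximate.

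**Conclusion.** The concern holds. As written, SAP 13.1 attaches to the EAIR an interval for a different rate, larger by the factor m. In a row with 100 affected subjects, an average of about 1.2 TEAEs each is enough for the interval to exclude the EAIR; with 10 affected subjects it takes about 1.63. These figures rest on unscaled Poisson Wald limits and need no assumption about exposure. Whether a given row crosses its threshold depends on an m that the documents do not give.

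The harm is confined to interval limits in rows with repeat events: the study is descriptive, with no hypothesis tests. It is still worth correcting before the tables are produced, because these are the only intervals on the safety results. The missing method for the EAIR difference is a separate gap in detail and adds nothing to the weight of this point.

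**What to change.** In SAP 13.1, replace the TEAE count as dependent variable with a subject-level 0/1 outcome: at least one TEAE in that row. State that the offset is the log of that subject's own exposure time. Two alternatives serve equally well: the number of affected subjects with the log of total within-arm exposure as offset, or an exact Poisson interval on that number (0.81 to 1.22 times the EAIR with 100 affected subjects). The arm total must not be used as the offset on individual records.

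Add one sentence naming the CI method for the EAIR difference, based on the same subject counts. If an event rate is also wanted, give it its own row, with an interval that allows for repeat events within a subject. The definition in SAP 5.5 stays as it is.

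The cost is one phrase, one sentence and a small programming change. No new data are needed and no EAIR point estimate changes.

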4.5.2. Exclusion Criteria

Subjects who meet any of the following exclusion criteria will be excluded from participation in this study:

1. Subjects who experienced a treatment-related AE or a serious AE (SAE) that precluded further treatment with ARQ-151 cream in studies ARQ-151-311 or ARQ-151-312 or ARQ-151-315.
2. Subjects that use any Excluded Medications and Treatments (see [Table 2](#)).
3. Subjects with skin conditions other than AD that would interfere with evaluations of the effect of the study medication on AD, as determined by the Investigator. Subjects with any condition on the treatment area which, in the opinion of the Investigator, could confound efficacy measurements (e.g., molluscum contagiosum).
4. Subjects with known genetic dermatological conditions that overlap with AD, such as Netherton syndrome.
5. Known allergies to excipients in ARQ-151 cream
[REDACTED]
6. Subjects who cannot discontinue the use of strong cytochrome P-450 CYP3A4 inhibitors e.g., indinavir, nelfinavir, ritonavir, clarithromycin, itraconazole, ketoconazole, nefazodone, saquinavir, suboxone and telithromycin during the study period.
7. Subjects who cannot discontinue the use of strong cytochrome P-450 CYP3A4 inducers e.g., efavirenz, nevirapine, glucocorticoids, barbiturates (including phenobarbital), phenytoin, and rifampin during the study period.

8. Known or suspected:
 - a. Severe renal insufficiency (defined as calculated creatinine clearance < 30mL/min)
Refer to the creatinine levels from the following visits:
 - ARQ-151-311/ARQ-151-312 studies: Screening Visit for subjects ages 6-11 and Baseline/Day 1 for subjects \geq 12 years old (for subjects 12-18 years old, if screening lab tests were collected within 3 weeks of Baseline/Day 1, screening results will be used)
 - ARQ-151-315 study: Screening Visit
 - b. moderate to severe hepatic disorders (Child-Pugh B or C)
 - c. history of severe depression, suicidal ideation or behavior
9. Females who are pregnant, wishing to become pregnant during the study, or are breast-feeding.
10. Subjects with any known serious medical condition (e.g., uncontrolled hypo- or hyper-thyroidism) or clinically significant laboratory abnormality that would prevent study participation or place the subject at significant risk, as determined by the Investigator.
11. Subjects with a history of chronic alcohol or drug abuse within 6 months of initiation of study medication.

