5.2 Baseline

There are two baseline definitions for the analyses:

- Primary baseline is defined as the last observation before or on the first dose of roflumilast cream 0.15% or 0.05% in ARQ-151 parent studies for subjects administered roflumilast previously and before or on the first dose of roflumilast cream 0.15% or 0.05% in this study* for subjects administered vehicle previously.
- OLE baseline is defined as the last observation before or on the first dose of roflumilast cream 0.15% or 0.05%* in this study.

If the last non-missing assessment was performed on the same date as the first dose of roflumilast cream* and time is not available, the assessment will be considered as baseline, except for adverse events (AEs) and medications starting on the first dose date which will be considered post-baseline. For subject local tolerability assessments, if the last non-missing assessment was performed on the same date as the first dose of roflumilast cream*, the assessment will be considered as baseline, regardless of the time of the assessment.

For the subjects administered vehicle in the parent study, the definition for Primary and OLE baselines are the same.

* Enrollment date (usually the Week 4 visit in the parent study) for enrolled subjects who discontinued early from this study before the first application of roflumilast cream 0.15% or 0.05%.

The following table ([Table 2](#)) described the baseline used in the analysis:

 Innovaderm Research	STATISTICAL ANALYSIS PLAN, Final Version 1.0
Protocol Number: ARQ-151-313	Sponsor: Arcutis Biotherapeutics, Inc.

Table 2 Summary of Primary/OLE Baseline in the Analyses

Analyses	Baseline*
Demographics and Baseline Characteristics	Primary baseline and OLE baseline, as applicable
Efficacy Analysis	Primary baseline and OLE baseline
Safety analysis for AEs and concomitant medications	OLE baseline
Safety analysis for clinical laboratory, vital signs, local tolerability assessments. PHQ-8, Modified PHQ-A, CDI-2, C-SSRS, and physical examination	Primary baseline

* Refer to Section 8 for more details.

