11 STUDY TREATMENT EXPOSURE AND TREATMENT COMPLIANCE

A summary of exposure to study treatment will be presented using the safety population by treatment group as defined in Section 5. It will include descriptive statistics on the number of days on OLE study treatment, as well as the number of study treatment applications based on diary, for each treatment group. Since subjects in the roflumilast arm of their parent study will simply be continuing the same treatment, their first treatment date will be the date of their week 4 visit in the parent study, even if study drug application was interrupted on that date. The number of days on study treatment in OLE study, will be calculated as follows:

$$(\text{Last treatment date in OLE} - \text{First treatment date in OLE}) + 1$$

For each subject, compliance (%) with study treatment will be calculated as follows:

$$\frac{\text{Number of study treatment applications}}{\text{Number of expected study treatment applications}} \times 100$$

Applied dose count and missed dose applications count were collected in eCRF study drug interruption module. Number of study treatment applications will be calculated as the sum of applied dose count.

Number of expected study treatment applications will be calculated as the sum of number of investigational product applications and number of doses missed. Of note, number of expected study treatment applications might change during the course of the study (refer to Section 3.1 for more details).

The number and percent of subjects who switch to a maintenance dosing schedule (BIW) at least once after week 4 will be provided by treatment group. The cumulative time and percent of time (Section 5.5) on the maintenance dosing schedule will be summarized only for those subjects who switched to BIW dosing at least once. The percent of time on the maintenance dosing schedule will also be summarized categorically as]0-25%],]25-50%],]50-75%], and >75%. The number of times each subject returned to QD dosing after switching to BIW dosing will be summarized categorically.

Subjects who roll over from the ARQ-151-315 study and turn 6 years old during the study will switch to Roflumilast cream 0.15% at their first scheduled post-birthday visit. The percentage of study days spent on each dose in this study will be summarized.

 Innovaderm Research ■■■	STATISTICAL ANALYSIS PLAN, Final Version 1.0
Protocol Number: ARQ-151-313	Sponsor: Arcutis Biotherapeutics, Inc.

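### The planned difference in exposure-adjusted AE rates sets subjects with 4 weeks on roflumilast against subjects just starting it, so it can move from zero with no real difference in drug risk.

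*SAP*

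**What the plan says.** SAP 13.1 reports the EAIR with a 95% CI in the SOC and PT tables of TEAEs and adds "the difference in EAIR between the 'Roflumilast cream 0.15%' and 'Vehicle / Roflumilast cream 0.15%' treatment groups", also with a two-sided 95% CI. Both groups are rollovers from ARQ-151-311/312.

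- **Rate.** SAP 5.5 defines the EAIR as ("number of subjects with an event / total within-arm exposure [days]) * 365.25 days/year * 100". This is one average over all exposure, not split by time on drug.
- **Start of counting.** A TEAE is "an AE that started post application of study medication at the Day 1 visit of study ARQ-151-313", or one already present that worsened on treatment. SAP 5.2 assigns the OLE baseline to AE analyses in both groups.
- **Prior drug.** SAP 11 says that "subjects in the roflumilast arm of their parent study will simply be continuing the same treatment". For the other group, SAP 5.2 says: "For the subjects administered vehicle in the parent study, the definition for Primary and OLE baselines are the same". Their first roflumilast dose is therefore in the OLE.
- **Entry.** Protocol 4.5.1 (criterion 3) requires completion of the parent study through Week 4. Protocol 4.5.2 (criterion 1) excludes "Subjects who experienced a treatment-related AE or a serious AE (SAE) that precluded further treatment with ARQ-151 cream". Neither rule is limited to one parent arm.
- **Interpretation.** SAP 6.1 plans no covariate adjustment, and SAP 5.7 plans no tests, with CIs for estimation only. SAP 5.5 and 13.1 do not align the groups on time since first dose and give no guidance on reading the difference.

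**The concern.** The two rates share a calendar origin but not a drug-exposure origin. The former-roflumilast rate starts in the fifth week of treatment, among people who got through the first four on drug. The former-vehicle rate includes those first four weeks, together with anyone who turns out not to tolerate roflumilast.

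TEAEs are a primary endpoint, and this is the only between-group difference with an interval that I can find in the SAP. Readers will look to it for an effect of prior treatment, or for evidence that tolerability improves with longer use. It could show either pattern purely because the groups start at different points in their time on drug.

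**Working it through.** The plan states no AE rate or EAIR difference, so there is no figure to reproduce. The check asks what the contrast gives when the drug carries exactly the same risk in both groups.

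**Inputs from the documents:** the EAIR formula (SAP 5.5), counting from OLE Day 1 (SAP 13.1), 4 weeks of prior drug in one group and none in the other (SAP 5.2, 11), and follow-up T of 24 or 52 weeks (SAP 3.1). The first 4 weeks are 4/24 = 16.7% or 4/52 = 7.7% of full-length follow-up.

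**Assumptions:** after 4 weeks on drug the rate of first events is h per year (0.05, 0.2 or 0.8). During the first 4 weeks it is r × h (r = 1, 2 or 3). Follow-up is complete.

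**Formulas,** with one week = 7/365.25 year:
- Former-roflumilast cumulative hazard: H = h × T × 7/365.25
- Former-vehicle cumulative hazard: H = h × (4r + T − 4) × 7/365.25
- EAIR per 100 subject-years: 100 × (1 − exp(−H)) / (T × 7/365.25)

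**Worked case, h = 0.2, r = 3, T = 24.** Exposure is 24 × 7/365.25 = 0.460 year.
- Former-roflumilast: H = 0.2 × 24 × 7/365.25 = 0.0920, EAIR 19.1
- Former-vehicle: H = 0.2 × 32 × 7/365.25 = 0.1227, EAIR 25.1
- Difference −6.0; inflation 25.1/19.1 − 1 = 31%

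**Results** (former-roflumilast v former-vehicle, per 100 subject-years; inflation of the latter in brackets, from unrounded rates):

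| h | r | 24 weeks | 52 weeks |
|---|---|---|---|
| any | 1 | equal (0%) | equal (0%) |
| 0.05 | 2 | 4.94 v 5.76 (16%) | 4.88 v 5.24 (7%) |
| 0.05 | 3 | 4.94 v 6.57 (33%) | 4.88 v 5.61 (15%) |
| 0.2 | 2 | 19.1 v 22.1 (16%) | 18.1 v 19.4 (7%) |
| 0.2 | 3 | 19.1 v 25.1 (31%) | 18.1 v 20.6 (14%) |
| 0.8 | 2 | 66.9 v 75.9 (13%) | 55.1 v 57.8 (5%) |
| 0.8 | 3 | 66.9 v 84.3 (26%) | 55.1 v 60.4 (9%) |

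The ratio of event rates, (4r + T − 4)/T, is the ceiling: for r = 3 it is 32/24 = 1.33 and 60/52 = 1.15. The subject-count EAIR stays below it because each subject counts once.

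**Effect on the interval.** Assume 950 ARQ-151-311/312 rollovers (about 400 + 2 × 275, from the protocol's summary of changes; not a stated total) and a prior-arm ratio of 2:1 or 1:1 (not stated). At h = 0.2 and r = 3, with a normal approximation, the 95% CI excludes zero in 23-27% of trials at 24 weeks and 13-14% at 52 weeks, against a nominal 5%.

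**Loss of intolerant subjects.** A second model has no general early excess. Instead 1-5% of subjects are susceptible, with an 86% chance of an event in their first 4 weeks on drug, and half or all of those affected leave. At h = 0.2 the differences are −1.5 to −9.6 at 24 weeks and −0.6 to −4.5 at 52 weeks.

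**Same contrast from OLE Day 29 in both groups.** Everyone then has at least 4 weeks on drug, and the windows are equal (20 or 48 weeks). At h = 0.2 the first model gives 19.3 v 19.3 and 18.3 v 18.3, a difference of zero. The second model also gives zero, because susceptible subjects leave only in their first 4 weeks on drug, which end before Day 29 in both groups.

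**The case against.** The strongest reply is that comparing continuing users with new starters is a legitimate descriptive contrast. The group labels show prior treatment, no test is planned, within-group EAIRs are reported alongside, and counting from OLE Day 1 puts both groups under the same dosing rules. That stands, and it limits the harm to misreading. It does not tell a reader what a non-zero interval means, because the SAP does not say.

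Three stronger readings are tempting and are not supported:

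- **That only the former-roflumilast group is selected.** Both entry rules apply to every rollover, so former-vehicle subjects have also been filtered, by 4 weeks of vehicle. Only selection on tolerance of the drug differs.
- **That the former-vehicle rate describes people new to the drug.** That holds for 4 of 24 or 52 weeks. The remainder is follow-up after the first month on drug, so any early excess is diluted.
- **That a bias has been shown.** No readable part of the documents gives AE rates by week on the cream. With a constant rate and no loss of intolerant subjects, the difference is zero.

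Starting former-roflumilast subjects at OLE Day 1 and former-vehicle subjects at Day 29 looks like the natural alignment, but it creates new mismatches. The windows become unequal, so a constant rate of 0.8 per year gives 66.9 v 68.9 (24 v 20 weeks) and 55.1 v 56.6 (52 v 48 weeks), where the current contrast gives zero. It would also keep the once-daily-only month (SAP 3.1) in one group and remove it from the other.

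**Conclusion.** The point holds as a conditional one. SAP 13.1 averages over a period in which the groups differ in time on drug and in prior selection for tolerating it, so the difference and its CI cannot be read as an effect of prior treatment or of longer use.

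Its size is unknown. For early-to-later rate ratios of 1 to 3 and later rates of 0.05 to 0.8 per year, inflation of the former-vehicle EAIR runs from 0% to about 33% over 24 weeks and from 0% to about 15% over 52 weeks. The upper figures are approached only for rare events. These ranges assume complete follow-up. With no early excess and no loss of intolerant subjects there is no distortion. As the contrast is descriptive, this should be corrected in the SAP, but it does not undermine the within-group safety results.

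**What to change.** In SAP 13.1, split the contrast by OLE period in both groups:

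1. Report the EAIR difference and 95% CI for TEAEs starting on or after OLE Day 29, with exposure counted from Day 29, among subjects still on treatment at Day 29 in both groups. The window and dosing rules then match, and everyone has at least 4 weeks on drug.
2. Report OLE Days 1-28 separately, labelled as new starters (former vehicle) versus continuing users (former roflumilast).
3. If the split is not made, drop the overall difference and its CI.

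The cost is SAP wording, one extra exposure cut and a slightly less precise contrast. No new data are needed, and the within-group EAIRs are unchanged. One limit remains: at Day 29 the groups have 4 and 8 weeks on drug, so an excess lasting beyond the first 4 weeks would not be fully removed. A footnote should say so.
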